3.2 Study Design

Prospective, single arm, feasibility (“ROLL-IN”) study of esmolol infusion in septic shock.

3.3 Objective

To assess the adequacy of subject identification and enrollment procedures. To assess the adequacy and efficiency of study protocols. To evaluate the estimates of coordinator burden for screening and enrollment.

3.5.1 Non-clinical outcomes for ROLL-IN:

1. Proportion of eligible patients consented
2. Proportion of protocol compliance
3. Amount of research coordinator time spent on different tasks

3.5.2 Anticipated primary clinical outcome for main trial: Organ-failure-free days at 28 days. Defined as the number of calendar days on which the patient receives none of (a) vasopressor therapy, (b) mechanical ventilation, or (c) renal replacement therapy. (Patients who die before 28 days will be assigned -1 organ-failure-free days in order to avoid making death equivalent to prolonged organ dysfunction.) For example, a patient who died on day 12 would have -1 organ-failure-free days, while a patient who resolved all organ dysfunction on day 9 but died on day 30 would be categorized as having 19 organ-failure-free days.

3.5.3 Anticipated secondary outcomes for main trial

1. All-cause hospital mortality
2. All-cause 28-day and 90-day mortality
 - a. Mortality will be ascertained through telephone followup for patients who were discharged alive before 90 days.
3. Peak serum high-sensitivity troponin
 - a. Troponin will be measured on day 0 and day 1.
4. 24-hour LV strain, as assessed by echocardiography
5. Days to transition to a quiescent vascular phenotype.
6. ICU-free days to day 28
 - a. Patients who die before 28 days will be assigned -1 ICU-free days, using a methodology similar to that used for organ-failure-free days.
7. Cardiogenic shock/requirement for inotropes through day 14. This is a binary variable and is met when any of the following is met
 - a. Dobutamine or milrinone infusion at any dose, lasting > 60 min
 - b. $CI \leq 2$ L/min/m² lasting > 30 min on NICOM
 - c. $ScvO_2 \leq 60\%$ on any measurement

3.6.2 Anticipated prespecified subgroups

1. Patients with abnormal LV strain on the initial echocardiogram (>-18%)
2. Patients with an abnormal tMPI (> 0.39) on the initial echocardiogram
3. Patients receiving an epinephrine infusion at the time of enrollment
4. Patients with a non-quiescent vascular phenotype at the time of enrollment
5. Patients over the age of 65 years

4.0 Study population and enrollment

The study will enroll 10 patients at one clinical center. Patients will be recruited from the ICUs of Intermountain Medical Center. The objective is to screen every newly admitted patient with septic shock to determine eligibility.

4.1 Screening

Appropriate subjects will be identified through review of the ER census and Intensive Care Unit (ICU) log several times a day, or by automated computer alerting, where available. Patients who are admitted from the ER of an outside hospital will be considered; patients transferred from an inpatient ward/ICU at an outside hospital will not be considered. Patients who are transferred to the ICU from a hospital ward of the study hospital will be considered if (a) sepsis was present at the time of admission to the hospital ward from the study hospital ER, and (b) the total time on the hospital ward was less than 24 hours. Permission to approach patients and/or their families will be requested from the clinical team caring for the patient. All patients meeting inclusion criteria will be entered into a screening log. Intermountain Medical Center has dedicated study physicians and coordinators who are certified and trained in human subjects protection and understand the study protocol. These individuals will oversee and/or perform screening and enrollment activities.

4.2 Inclusion Criteria

Subjects will be considered eligible for the study when they are older than 18 years of age, admitted to an ICU with septic shock, and for at least an hour, they are receiving vasopressors through a central venous catheter and have a heart rate > 90/min. Subjects must meet the heart rate and vasopressor criteria at the time of enrollment.

Inclusion Criterion	Justification/Description
Age ≥ 18 years	Children are physiologically distinct from adults
Septic shock	Meets consensus criteria: 
 ≥2 SIRS criteria Suspected or confirmed infection Receiving vasopressor infusion to treat hypotension after at least 20ml/kg intravenous crystalloid volume expansion
Adequately volume expanded	Designed to include only non-compensatory tachycardia, that which persists after adequate volume expansion. Being no longer fluid responsive requires any one of 
 CVP > 15 mmHg Negative Passive Leg Raise (PLR) maneuver (< 10% increase in cardiac output during PLR) Stroke volume increase < 10% in response to rapid (< 5 min) infusion of at least 250 ml crystalloid solution In patients being passively mechanically ventilated, stroke volume variability (measured by a valid method, including NICOM) < 10%
Receiving vasopressor infusion via central venous catheter	At least 60 min of any infusion rate of norepinephrine, epinephrine, vasopressin, or phenylephrine
Current or imminent placement of arterial catheter	Allows continuous measurement of blood pressures during esmolol infusion and is standard in the study ICU.
Tachycardia (>90/min)	Heart rate must remain > 90/min for at least one hour, while the patient is receiving vasopressors

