2.5 Inclusion criteria

1. Age \geq 18 years
2. Within 48 hours of admission to the ICU and septic shock (sepsis present at time of admission)
 - a. Septic shock defined by consensus criteria as
 - i. At least two SIRS criteria
 - ii. Suspected or documented infection
 - iii. Receiving vasopressors to treat hypotension after at least 20 ml/kg intravenous crystalloid volume expansion
3. Receiving vasopressors through a central venous catheter for more than 60 minutes.
4. Arterial catheter in place or expected to be placed imminently.
5. Heart rate $>$ 90/min while receiving vasopressors for more than 60 minutes.
6. Adequately volume expanded, as manifest by any of the following, performed as part of routine clinical care (i.e., no study procedures will be performed before signed consent). **If none of these measures are clinically available, the clinical attending must confirm that volume expansion is adequate.** (After enrollment, a final safety check will confirm the adequacy of volume expansion.)
 - a. Central venous pressure (CVP) $>$ 15 mm Hg.
 - b. Negative Passive-Leg Raise (PLR) maneuver ($<$ 10% increase in cardiac output after PLR).
 - c. No cardiac output response ($<$ 10% increase) after rapid infusion ($<$ 5 min) of 250 ml of IV crystalloid (i.e., a graded volume expansion challenge [GVEC]).
 - d. For patients who happen to be breathing passively on a positive pressure mechanical ventilator delivering at least 8 ml/kg tidal volumes and in normal sinus rhythm, stroke volume variability $<$ 10% (such patients are acknowledged to be uncommon; *the protocol does not recommend or require the induction of passive breathing*).

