5.1.1.3 Review of fluid responsiveness/adequacy of volume expansion

After the lack of cardiogenic shock has been confirmed and still before esmolol infusion, subjects will be evaluated for fluid responsiveness. Once the subject has been determined to no longer be fluid responsive, applying the tests outlined in section 4.2, esmolol will be infused. If, in the investigator's best judgment, one of those markers of fluid responsiveness is providing a false negative result, s/he may require additional volume expansion, in consultation with the treating team, before initiation of esmolol infusion.

Figure 2

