5.1.2 Ventilator management

ARDS Network low-stretch ventilation (as is the standard at IMC) will be used for all mechanically ventilated patients, given the proportion of patients with septic shock who have ARDS and evolving data suggesting that patients at risk for ARDS merit low-stretch ventilation. Ventilator weaning will be performed as per institutional protocol. Weaning will not wait until esmolol infusion has ceased.

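### Section 4.2, whose tests release esmolol, omits the 8 ml/kg tidal-volume condition that section 2.5(6d) sets for the same stroke volume variability test

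*Combined protocol and SAP*

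**What the plan says.** Section 2.5, item 6, lists four measures of adequate volume expansion. The fourth, 6d, is SVV below 10%. It is limited to patients who happen to be breathing passively on a "positive pressure mechanical ventilator delivering at least 8 ml/kg tidal volumes and in normal sinus rhythm". The item adds that such patients are uncommon and that passive breathing is not to be induced for the purpose.

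Section 4.2 lists the same four kinds of test in its table. Its SVV entry reads "In patients being passively mechanically ventilated, stroke volume variability (measured by a valid method, including NICOM) < 10" percent. The rule above the list is "Being no longer fluid responsive requires any one of" the four.

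Section 5.1.1.3 governs the step just before dosing. Once a subject is found no longer fluid responsive, "applying the tests outlined in section 4.2, esmolol will be infused". It does not refer to 2.5. It adds that if the investigator judges that "one of those markers of fluid responsiveness is providing a false negative result", more volume may be required before esmolol.

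Two further provisions of 2.5(6) affect who reaches that step without a listed measure: "If none of these measures are clinically available, the clinical attending must confirm that volume expansion is adequate", and after enrollment "a final safety check will confirm the adequacy of volume expansion".

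On ventilation, section 5.1.2 says "ARDS Network low-stretch ventilation (as is the standard at IMC) will be used for all mechanically ventilated patients". It gives no ml/kg value.

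**The concern.** Section 4.2 says the volume criterion is there so that only tachycardia that is not compensating for low volume is treated. A beta-blocker is then given to slow that heart rate. The fluid-responsiveness check is thus a pre-dose safety gate, and its conditions should be the same wherever the protocol states them.

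They are not the same for SVV. The section that sets eligibility restricts the test to certain ventilator settings and a certain rhythm. The section that the release rule points to drops both restrictions. Staff who follow 5.1.1.3 literally would apply the looser version.

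There is also a consequence for what the roll-in is meant to measure. Section 2.8 treats compliance with the final safety check as adequate only at 100%. A patient cleared on SVV at a tidal volume below 8 ml/kg satisfies 4.2 and 5.1.1.3, yet rests on a reading that 2.5(6d) does not admit. Whether that check was compliant would be open to dispute, in a study of at most 10 patients.

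**Working it through.** This is a comparison of texts. The plan gives no figure to reproduce, and no sample-size or error-rate calculation applies.

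**Step 1. Set the two versions side by side.**

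| Element of the SVV test | 2.5(6d) | 4.2 |
|---|---|---|
| Threshold | below 10% | below 10% |
| Passive breathing on the ventilator | required | required |
| Tidal volume of at least 8 ml/kg | required | not stated |
| Normal sinus rhythm | required | not stated |
| Valid measurement method | not stated | required |

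Of the 3 patient conditions in 2.5(6d), 4.2 keeps 1 and omits 3 − 1 = 2. The valid-method wording in 4.2 concerns how SVV is measured. It does not restore a ventilator setting.

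**Step 2. Ask whether another visible provision covers each omission.**

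- *Rhythm: largely covered.* Section 2.6 excludes known or current atrial fibrillation, sick sinus syndrome, a PR interval above 200 msec, Grade 2 or 3 heart block, and a pacemaker. Section 2.4 adds a telemetry and EKG review at the final safety check.
- *Tidal volume: not covered.* No visible text carries the 8 ml/kg floor into 4.2 or 5.1.1.3. Section 5.1.2 sets a ventilation strategy without a number.

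**Step 3. Ask which version controls dosing.** Section 5.1.1.3 names 4.2. Under 4.2 one passing test is sufficient. So SVV alone can release esmolol, on the 4.2 wording.

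**Step 4. Ask whether enrollment has already closed the gap.** Not always. Take a patient for whom none of the 2.5(6) measures is clinically available:

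1. The attending confirms that volume expansion is adequate, and the patient is enrolled.
2. The final safety check excludes cardiogenic shock (5.1.1.2).
3. Fluid responsiveness is then assessed by the 4.2 list. For this patient it is the first listed test applied.
4. The patient is passively ventilated below 8 ml/kg and SVV reads below 10%. No other listed test has been passed.
5. Under 4.2 and 5.1.1.3 esmolol starts. Under 2.5(6d) this SVV reading would not count, and central venous pressure, passive leg raise or a fluid challenge would be needed.

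**Step 5. Ask how many patients this affects.** That would need the share of enrolled patients who are passively ventilated, the share of those below 8 ml/kg, and the share of those who pass on SVV alone. The documents give none of the three, so no count or probability can be supported.

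**The case against.** The strongest case on the other side has four parts.

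*Figure 2 may hold the condition.* Section 5.1.1.1 says the post-enrollment check follows Figure 2, which is not shown. This stands as a limit: the conflict between 2.5 and 4.2 can be verified, but what Figure 2 requires cannot. It does not remove the point, because if Figure 2 states the floor, 4.2 and 5.1.1.3 contradict it and still need correcting.

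*The sections can be read together.* The 4.2 table restates and justifies 2.5, and nothing says that it overrides 2.5, so a careful physician would apply the narrower conditions. That is a reasonable guess at intent. However, 5.1.1.3 points to 4.2 alone, and a safety gate should not depend on the reader combining two versions.

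*The failure is anticipated.* The investigator may require more volume when a false negative is suspected. This helps, but it is discretionary and names no tidal-volume trigger.

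*Other safeguards limit the harm.* This largely stands. Septic shock entry requires at least 20 ml/kg of crystalloid. Ejection fraction, ScvO₂ and NICOM cardiac index are checked before fluid responsiveness. Because NICOM is already in use, a passive leg raise judged by cardiac output should often be feasible, which makes reliance on SVV alone less likely. After the start, Appendix 1 uses no bolus, calls for immediate volume evaluation when urine output is low or vasopressor dose rises, bars up-titration during such an event, and sets STOP rules. These later rules act only once exposure has begun.

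A reader might also infer that low-stretch ventilation puts most ventilated patients below 8 ml/kg, so the gap would arise often. The documents do not support that: 5.1.2 gives no ml/kg figure, and passive breathing is not induced.

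**Conclusion.** The concern holds as a conflict within the protocol at a pre-dose safety gate. The same SVV threshold carries three patient conditions in 2.5(6d) and one in 4.2, and the visible release rule uses 4.2. Of the two omitted conditions, tidal volume is the one that matters, because rhythm is largely covered elsewhere.

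The reach is small. It is confined to passively ventilated patients below 8 ml/kg who pass on SVV alone, within a single-arm study of up to 10 patients. Its frequency cannot be estimated from the documents.

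A reader might go further and conclude that esmolol will be given to patients who still need volume. The documents do not show this. They do not say how tidal volume changes an SVV reading, and a patient cleared outside the 2.5(6d) conditions is not thereby shown to be fluid responsive. What is established is only that the text permits clearance on a reading that the protocol elsewhere does not accept.

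The conclusion rests on the visible text, with Figure 2 unseen. The correction should be made: it uses the protocol's own condition and costs little.

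**What to change.** Reword the SVV item in the 4.2 table so that it applies only to patients who are passively ventilated, receive tidal volumes of at least 8 ml/kg and are in normal sinus rhythm. Keep the 10% threshold and the existing wording on a valid method, including NICOM. Because 5.1.1.3 cites 4.2, the release check changes with it. Make Figure 2 match.

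Patients outside these conditions use central venous pressure, passive leg raise or the fluid challenge. All three are already in 4.2 and need no change for this point.

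The edit is one table cell and a check of one figure. In use, an occasional patient will need another listed test. If that test is the fluid challenge, the patient receives at least 250 ml more crystalloid, and esmolol may start a little later.

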4.3 Exclusion Criteria

Exclusions are designed to protect patient safety and maximize scientific integrity. They primarily relate to individuals who may not tolerate β -blockade. Coenrollment in other interventional studies will not be allowed.

4.3.1 List of Exclusions and Reason for Exclusions

Exclusion Criterion	Justification/Description
Cardiogenic shock	Safety consideration: β -blockade may worsen preexisting cardiogenic shock. Cardiogenic shock defined as any one of 
 Cardiac Index ≤ 2 L/min/m² ScvO₂ $\leq 60\%$ Ejection Fraction $\leq 25\%$ Current infusion of any dose of dobutamine, milrinone, or dopamine Current infusion of epinephrine to treat clinically diagnosed cardiogenic shock.
Preexisting heart block	Safety consideration: β -blockade may worsen heart block. Defined as any of the following 
 Sick sinus syndrome PR interval > 200 msec Any current evidence or history of Grade 2 or Grade 3 heart block Pacemaker or plans to place a pacemaker
Atrial fibrillation at time of enrollment	Substantial noise associated with exposure, hemodynamic measurements, and outcomes; may require independent heart rate control or cardioversion.
Current nodal blockers or anti-arrhythmic agents	Safety consideration: risk of excess nodal blockade. Increased experimental noise. Receipt of any of the following within 3 half lives (see full list in Appendix) 
 Non-dihydropyridine calcium channel blockers Digitalis Anti-arrhythmics (e.g., amiodarone, dronedarone, mexiletine) Beta blockers
Receiving clonidine, guanfacine, or moxonidine	Safety issue
Moderate or severe pulmonary hypertension	Possible safety consideration; risk of hemodynamic deterioration. Defined as a documented history of prior right heart catheterization or current evidence on TTE of any of the following. 
 mPAP ≥ 35 mmHg SPAP ≥ 60 mmHg
Allergy to esmolol or vehicle	Rare, but required for patient safety.
Admitted for hospice or comfort care	Incomplete and biased data on both exposure and outcome.
Inability to obtain consent within 48 hours of ICU admission	This study does not qualify for waiver of consent
Active pregnancy or nursing	Physiology of pregnant patients distinct; potential risks to fetus unknown; drug levels in breast milk.
Prisoners	Septic shock is not specific to prisoners, so ethical concerns emphasize the protection of autonomy.
Previously enrolled in this trial	Violation of the independence assumption.
Pheochromocytoma or status asthmaticus	Safety issue associated with beta blockade
Hemoglobin < 7 gm/dl	Exclude anemia as cause of tachycardia; avoid risk of impaired oxygen delivery related to anemia
Cardiovascular collapse	Safety consideration; failure to achieve 65mmHg MAP with vasopressors.

Cardiac arrest within 24 hours	Safety consideration
Worse than moderate aortic stenosis	Known aortic stenosis, with any of (1) mean gradient ≥ 40 mmHg OR (2) maximum gradient ≥ 60 mmHg OR (3) aortic valve area ≤ 1.0 cm ² OR (4) aortic valve area index ≤ 0.85 cm ² /m ² body surface area. This is a hypothetical safety consideration.
Worse than mild mitral stenosis	Known mitral stenosis, with any of (1) valve area ≤ 1.5 cm ² OR mean gradient ≥ 5 mmHg. This is a hypothetical safety consideration.

4.4 Enrollment Time Window

Patients must be enrolled within 48 hours of ICU admission and septic shock and must still meet inclusion criteria at the time of enrollment.

4.5 Women and Minorities

Every effort will be made to assure adequate representation of women and minorities. The study inclusion and exclusion criteria (other than the pregnancy exclusion) do not differentially exclude women or minorities.

5.0 Study Procedures

[figure not shown]
5.1 Common Management Strategies

5.1.1 Study Startup Procedures

Potential candidates will be screened according to the algorithm outlined in FIGURE 1. A study investigator will review, with the research coordinator, all study inclusions and exclusions before consent and enrollment.

Figure 1

EVALUATING INCLUSION CRITERIA

5.1.1.1 Review for final exclusions

A study investigator will review, with the research coordinator, all study inclusions and exclusions before consent and enrollment. After enrollment, according to the protocol depicted in FIGURE 2, study personnel will confirm that cardiogenic shock is absent and adequate volume expansion has occurred. These evaluations are performed after consent because they involve study procedures, which cannot be required of subjects who have not consented. If cardiogenic shock is documented at this point, a subject will be followed for outcomes and biomarkers but esmolol will *not* be infused. After the final safety check has been completed and the patient is confirmed eligible for study drug infusion, study drug infusion should be started as soon as possible and within 3 hours of passing the final safety check.

[figure not shown]
5.1.1.2 Evaluation for cardiogenic shock

If cardiogenic shock is documented at this point, a subject will be followed for outcomes and biomarkers but esmolol will not be administered. This step involves evaluation of LV ejection fraction, measurement of ScvO₂, and direct measurement of cardiac index using the NICOM bioreactance device.

5.1.1.3 Review of fluid responsiveness/adequacy of volume expansion

After the lack of cardiogenic shock has been confirmed and still before esmolol infusion, subjects will be evaluated for fluid responsiveness. Once the subject has been determined to no longer be fluid responsive, applying the tests outlined in section 4.2, esmolol will be infused. If, in the investigator's best judgment, one of those markers of fluid responsiveness is providing a false negative result, s/he may require additional volume expansion, in consultation with the treating team, before initiation of esmolol infusion.

Figure 2

5.1.2 Ventilator management

ARDS Network low-stretch ventilation (as is the standard at IMC) will be used for all mechanically ventilated patients, given the proportion of patients with septic shock who have ARDS and evolving data suggesting that patients at risk for ARDS merit low-stretch ventilation. Ventilator weaning will be performed as per institutional protocol. Weaning will not wait until esmolol infusion has ceased.

5.1.3 Baseline Assessment

In addition to the evaluation for inclusion and exclusion criteria, the following parameters will be obtained on all subjects. Unless otherwise specified, measurements will be those closest in time to enrollment.

- Full TTE, including strain measurements
- Serum for troponin
- Plasma for vascular biomarkers (e.g., angiotensin)
- Heart rate variability
- Vasoactive medications (e.g., agent, infusion rate)
- Vital signs
- Ventilator settings (e.g., PEEP, PF or SF ratio, tidal volume, plateau pressure)
- Admission APACHE II/IV score and components
- SOFA scores and constituents
- Age
- Sex
- Race/ethnicity
- Contact information

5.1.4 24-hour assessment, including early protocol

- Full TTE, including for strain
- Serum for vascular biomarkers, including Troponin
- Heart rate variability
- Vasoactive medications (e.g., agent, infusion rate)
- SOFA scores and constituents
- APACHE II/IV score and constituents
- Vital signs
- Ventilator settings (e.g., PEEP, PF or SF ratio, tidal volume, plateau pressure)

